6.3 Lifestyle Restrictions

There are no lifestyle restrictions applicable for this study given that the participants will receive the study investigational products (IPs) IV.

6.4 Screen Failures

Screen failures are defined as participants who consent to participate in the clinical study but are not subsequently randomized/entered in the study. A minimal set of screen failure information is required to ensure transparent reporting of screen failure participants and to respond to queries from regulatory authorities. Minimal information includes date of consent, demography, screen failure details, eligibility criteria, and any serious AEs.

6.4.1 Retesting During Screening Period

This study permits the re-enrollment of a participant who has discontinued the study as a pretreatment failure (ie, participant has not been randomized/has not been treated). If re-enrolled, the participant must be re-consented.

Retesting of laboratory parameters and/or other assessments during the extended screening period will be permitted (in addition to any parameters that require a confirmatory value).

The most current result prior to randomization is the value by which study inclusion will be assessed, as it represents the participant's most current clinical state.

Laboratory parameters and/or assessments that are included in Table 2-1, Screening Schedule of Activities, may be repeated in an effort to find all possible well-qualified participants. Consultation with the Medical Monitor (or designee) may be needed to identify whether repeat testing of any particular parameter is clinically relevant.

Testing for asymptomatic SARS-CoV-2 infection, (eg, by reverse transcriptase polymerase chain reaction (RT-PCR) or viral antigen) is not required. However, some participants may develop suspected or confirmed symptomatic SARS-CoV-2 infection or be discovered to have asymptomatic SARS-CoV-2 infection during the screening period. In such cases, participants may be considered eligible for the study after meeting all inclusion/exclusion criteria related to active infection, and after meeting the following criteria:

- At least 10 days (20 days for severe/critical illness) have passed since symptoms first appeared or positive RT-PCR or viral antigen test result, and
- At least 24 hours have passed since last fever without the use of fever-reducing medications, and
- Acute symptoms (eg, cough, shortness of breath) have resolved, and
- In the opinion of the investigator, there are no COVID-19-related sequelae that may place the participant at a higher risk of receiving investigational treatment, and
- Negative follow-up SARS-CoV-2 RT-PCR or viral antigen test based on institutional, local or regional guidelines

7 TREATMENT

7.1 Treatments Administered

Study treatment is defined as any investigational treatment(s), marketed product(s), placebo, or medical device intended to be administered to a study participant according to the study randomization or treatment allocation.

An IP, also known as investigational medicinal product in some regions, is defined as a pharmaceutical form of an active substance or placebo being tested or used as a reference in a clinical study, including products already with a marketing authorization but used or assembled (formulated or packaged) differently from the authorized form, or used for an unauthorized indication, or when used to gain further information about the authorized form.

Other medications used as support or escape medication for preventative, diagnostic, or therapeutic reasons, as components of the standard of care for a given diagnosis, may be considered as non-IPs.

In this protocol, IPs are the following:

- BMS-986249
- Nivolumab
- Ipilimumab

All 3 drugs used in this open-label study qualify as IPs, per previous text, and their description and storage information are described in Table 7.1-1.

Table 7.1-1: Study Treatments for CA030001

Product Description / Class and Dosage Form	Potency	IP/Non-IMP	Blinded or Open Label	Packaging / Appearance	Storage Conditions (per Label)
BMS- 986249-01 for injection	160 mg/vial (40 mg/mL)	IP	Open label	Vial	Store at 2°C to 8°C. Protect from light and freezing
nivolumab (BMS-936558) solution for injection	100 mg/vial (10 mg/mL)	IP	Open label	Vial	Store at 2°C to 8°C. Protect from light and freezing.
ipilimumab (BMS-734016) solution for injection	200 mg/vial (5 mg/mL)	IP	Open label	Vial	Store at 2°C to 8°C. Protect from light and freezing.
ipilimumab (BMS-734016) solution for injection	50 mg/vial (5 mg/mL)	IP	Open label	Vial	Store at 2°C to 8°C. Protect from light and freezing.

Abbreviations: IMP = investigational medicinal product, IP = investigational product.

7.1.1 Schedule of Dose for Each Investigational Product

The dosing schedule for each IP is detailed below in Table 7.1.1-1 for all study parts. Planned dose levels may be modified (eg, change in administration schedule) or intermediate dose levels may be added, based upon evaluation of available safety, PK, and data.

All participants will be monitored continuously for AEs while on study treatment. Treatment modifications (eg, dose delay or discontinuation) will be based on specific laboratory and AE criteria, as described in Section 7.5.

Table 7.1.1-1: Selection and Timing of Dose for All Study Parts

Study Treatment ^a	Flat Dose Levels	Frequency of Administration	Route of Administration	Minimal Infusion Time ^b (Minutes)		
BMS-986249 monotherapy	240 - 800 mg	Q4W	IV	30		
BMS-986249 monotherapy	1,600 mg	Q4W or Q8W	IV	120		
BMS-986249 monotherapy	2,400 mg	Q4W	IV	180		
BMS-986249	240 mg - 800 mg	Q4W or Q8W	IV	120		
+ nivolumab	+ 480 mg					
Co-administration						
BMS-986249	1,200 mg	Q4W or Q8W	IV	120 ^c		
+ nivolumab	+ 480 mg			120		
Co-administration	_					
BMS-986249	1,600 mg	Q4W or Q8W	IV	180		
+ nivolumab	+ 480 mg					
Co-administration	_					
nivolumab monotherapy	480 mg	Q4W	IV	30		
BMS-986249 + nivolumab Co-administration	240 mg + 360 mg	Q3W x 4 doses	IV	60		
(Combination Therapy Phase, Cycles 1-4)						
Followed by nivolumab monotherapy ^d	480 mg	Q4W	IV	30		
(Maintenance Phase, Cycle 5 and beyond)						
Ipilimumab	3 mg/kg	Q3W x 4 doses	IV	30		
+ nivolumab ^e	+ 1 mg/kg	Q3W x 4 doses	IV	30		
(Combination Therapy Phase, Cycles 1-4)						
Followed by nivolumab monotherapy ^d	480 mg	Q4W	IV	30		
(Maintenance Phase, Cycle 5 and beyond)						

Abbreviations: IV = intravenous; Q3W = every 3 weeks; Q4W = every 4 weeks; Q8W = every 8 weeks.

- a Additional dose levels and/or schedules may be explored
- b If needed, flush the IV line with an appropriate amount of diluent (eg, 0.9% sodium chloride or 5% dextrose in water) to ensure that the complete dose is administered over the approximate designated infusion time.
- c For participants < 35 kg receiving 1,200 mg BMS-986249 in combination with 480 mg nivolumab, the minimum infusion time will be approximately 180 minutes.
- d The nivolumab monotherapy Maintenance Phase will begin 3 weeks after the last BMS-986249 or ipilimumab and nivolumab Combination Therapy Phase (Cycles 1-4) dose.

Protocol Amendment No.: 09

Date: 14-Mar-2023

e Ipilimumab and nivolumab will be administered sequentially as 2 separate IV infusions. Nivolumab will be given first, over approximately 30 minutes, followed by ipilimumab over approximately 30 minutes, beginning at least approximately 30 minutes after completion of the infusion of nivolumab.

BMS-986249 infusions, as a monotherapy or co-administration, will require a 60-minute observation period following the first 3 infusions for each participant.

Additional preparation, administration, storage/handling and infusion details for BMS-986249, ipilimumab, and nivolumab are provided in the Pharmacy Manual.

7.2 Method of Treatment Assignment

Participants will be enrolled using an Interactive Response Technology (IRT) system; until this system is activated, enrollment will be manually managed by the Sponsor.

During dose escalation, all participants will be assigned to Part 1A until the decision is made to escalate to the third dose cohort. Subsequently, treatment in Part 1B will be initiated, and dose escalation in the 2 parts will occur in parallel. Treatment assignments for participants eligible for both Part 1A and Part 1B will prioritize Part 1B through IRT whenever possible. If there are no openings in Part 1B, then the participant will be assigned to the next open part/cohort. Prioritization of participants eligible for both Part 1A and Part 1B may be modified to ensure the dose of Part 1B does not exceed the highest tolerated dose in Part 1A. If Part 1 is open upon the decision to initiate Part 2, treatment in the 2 parts will occur in parallel. Treatment assignments for participants eligible for Part 1A or Part 1B, and Part 2 will prioritize Part 2 through IRT whenever possible. If there are no openings in Part 2, then the participant will be assigned to the next open part/cohort.

In the BMS-986249 in Combination with Nivolumab Randomized Cohort Expansion in Melanoma (Part 2A) every participant that signs the informed consent form will be assigned a participant identification number in IRT. In order to be randomized, pre-treatment tumor tissue obtained in the metastatic setting or from an unresectable site of disease must be provided for biomarker analyses. A participant must have quantifiable PD-L1 expression (≥ 1% or < 1% tumor cell membrane staining) or be classified as PD-L1 indeterminate. Participants will be stratified by PD-L1 expression and M-stage. Participants meeting eligibility criteria were to be randomized in a 1:1:1:1:1 ratio to Arms A - E. As of Revised Protocol 07, further enrollment/randomization into Part 2A Arms A, B, and E is closed, and Arm F is added. Across study randomization for Part 2A participants meeting eligibility criteria will randomize in approximately a 1:1:1 ratio to open arms (eg, Part 2A Arms C, D, and F). If there is a change to randomization (eg, discontinuation of an

Arm or temporarily holding enrollment into an Arm while evaluation is ongoing), the adjusted randomization schedule will be documented by a note to file or administrative letter. Within 7 working days from randomization, the participant must receive the dose of study medication, unless otherwise agreed upon with the Medical Monitor (or designee). BMS will create a randomization schedule which will be uploaded into the IRT.

In the BMS-986249 in Combination with Nivolumab Additional Tumor Cohort Expansion (Part 2B) every participant that signs the informed consent form will be assigned a participant identification number in IRT. Participants will be assigned to a tumor-type specific cohort of HCC, CRPC, or TNBC, respectively.

For Part 1, participants will not be replaced if they are discontinued from the study secondary to an AE unless the AE can be determined to be unrelated to treatment.

For Part 2, participant replacement will not be allowed for participants who are discontinued after dosing.

Study treatment will be dispensed at the study visits as listed in the Schedule of Activities (Section 2).

7.3 Treatment Duration

Participants will be treated for up to 2 years in all study parts (see Section 5.4.4 for rationale).

7.4 Blinding

This is an open-label study and randomized in Part 2A. Designated staff of the Sponsor may receive access to treatment codes prior to database lock to facilitate early exploratory data analysis and the bioanalytical analysis of PK samples and immunogenicity. A bioanalytical scientist in the Sponsor's Bioanalytical Sciences department (or a designee in the external central bioanalytical laboratory) will have access to the randomized treatment assignments in order to minimize unnecessary bioanalytical analysis of samples. In addition, the Sponsor's Research and Development team will have access to the treatment codes prior to final data base lock for ongoing evaluation of preliminary available data (eg, safety, PK, and

7.5 Dosage Modification

Intra-participant dose escalation/reduction of BMS-986249, nivolumab, or ipilimumab is not permitted in this study in order to allow better evaluation of the safety and efficacy at individual dose levels and schedules.

7.5.1 Dose-limiting Toxicities

For the purpose of guiding dose escalation, DLTs will be defined based on the incidence, intensity, and duration of AEs that are possibly related to study treatment. The DLT period will be 5 weeks (35 days) in both BMS-986249 monotherapy and combination dose escalation (Parts 1A and 1B). Any toxicities that occur beyond the DLT period will be accounted for in making final dose level decisions. Participants who have received 2 doses of BMS-986249 and have completed or discontinued due to a DLT in the 5-week DLT period will be considered as DLT-evaluable participants for BMS-986249 monotherapy. Participants receiving either 2 dosing visits of

Protocol Amendment No.: 09

Date: 14-Mar-2023

BMS-986249 and nivolumab, or participants who discontinued due to a DLT in the 5-week combination treatment DLT period, will be considered as DLT-evaluable participants for combination treatment. Participants who withdraw from the study during the DLT evaluation period or have received less than 2 dosing visits for reasons other than a DLT in both monotherapy and combination therapy will not be considered as DLT-evaluable participants and may be replaced with a new participant at the same dose level. Participants who are dose delayed during the DLT evaluation period for reasons other than a DLT in both monotherapy and combination therapy will be considered as DLT-evaluable participants if they received at least 2 doses of therapy.

For the purpose of participant management, any drug-related AE that meets DLT criteria, regardless of the cycle or cohort (including Part 2) in which it occurs, will lead to discontinuation of study treatment. The incidence of DLT(s) during the 5-week DLT evaluation period will be used in dose escalation decisions and to define the MTD. AEs occurring after the DLT period will be considered for the purposes of defining the recommended Phase 2 dose of BMS-986249 (RP2D) upon agreement between the Sponsor, Medical Monitor (or designee), and investigators.

AEs will be graded according to the NCI CTCAE v4.03.

Part 1B participants with NSCLC will only be evaluated in a cohort once the initial DLT evaluation for that cohort has been completed.

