10 STATISTICAL CONSIDERATIONS

10.1 Sample Size Determination

10.1.1 Dose Escalation

Dose escalation in Part 1A (BMS-986249 monotherapy) and Part 1B (BMS-986249 combination therapy with nivolumab) will be guided by BLRM employing the EWOC principle. The BLRM method is fully adaptive; makes use of all the information available at the time of each dose assignment, not just data from the current dose level; and directly addresses the ethical need to control the probability of overdosing. Furthermore, the BLRM uses the knowledge gained from participants treated with ipilimumab (for Part 1A) or ipilimumab in combination with nivolumab (for Part 1B). The use of the EWOC principle limits the risk of exposing participants in the next cohort to an intolerable dose by ensuring that the posterior probability of
the DLT rate exceeding at any dose is capped at
Approximately 4 participants (3 + 1) will be treated at the starting dose levels of BMS-986249 alone or BMS-986249 in combination with nivolumab. While the BLRM will use DLT information from the DLT period only, clinical assessment will take into consideration the entirety of available preliminary data, including PK/ from all treated participants in assigning a dose level for the next cohort of 3 participants. AEs meeting DLT criteria outside of the 5-week DLT period may also be incorporated into the BLRM and dose de-escalation may be considered as appropriate based on the BLRM recommendation. At least 6 DLT-evaluable participants will be treated at the BLRM-recommended MTD (BLRM-MTD). A maximum of 12 DLT-evaluable participants will be treated at each dose level. Once the BLRM-MTD is identified, then additional participants may be treated at the BLRM-MTD or any dose level below the BLRM-MTD for further evaluation of safety, PK, or parameters as required. The maximum number of participants to be treated will be up to 45 for Part 1A (BMS-986249 monotherapy) and up to 60 for Part 1B (BMS-986249 combination therapy with nivolumab).
The BLRM-MTD is the dose that satisfies the following 3 conditions:

- The empirical posterior probability that the "DLT rate of 16% to pre-specified value (ie, 50%).
- This probability needs to be the largest among the dose levels that satisfy the EWOC condition
- A minimum number of participants (ie, 6) was treated at this dose level.

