Detailed in the tables below are the on-treatment schedule of activities and pharmacokinetic (PK) sampling schedule for potential alternative every-8-weeks (Q8W) BMS-986249 dosing administration that may be explored in The Dose Escalation Phase (Part 1) of CA030001 following evaluation of preliminary available safety, PK, and data and upon discussion and agreement between the Investigators and Medical Monitor (or designee) (Section 5 main protocol). The alternative dosing schedule in Part 1 was initially initiated via administrative letter 03 to evaluate 1600 mg BMS-986249 Q8W monotherapy in Part 1A, and via administrative letter 04 to evaluate 800 mg BMS-986249 Q8W + 480 mg nivolumab Q4W combination therapy in Part 1B.

- Table 1: On-Treatment Schedule of Activities for BMS-986249 Q8W Dosing Schedule in the Dose Escalation Phase (Part 1) in CA030001
- Table 2: PK and ADA Sampling Schedule for Part 1A BMS-986249 Q8W Monotherapy in Dose Escalation in CA030001
- Table 3: PK and ADA Sampling Schedule for Part 1B BMS-986249 Q8W Combination in Dose Escalation in CA030001

Table 1: On-Treatment Schedule of Activities for BMS-986249 Q8W Dosing Schedule in the Dose Escalation Phase (Part 1) in CA030001

Procedure	Cycle 1 (28 days in length)			n)	Cycle 2 (28 days in length)			Cycles 3 and Beyond (each cycle 28 days in length)	EOT ^{a,b}	Notes	
rrocedure	D1	D8	D15	D22	D1	D8	D15	D22	D1	EOI	Notes
		(± 2 days)	(± 2 days)	(± 2 days)	(± 2 days)	(± 2 days)	(± 2 days)	(± 2 days)	(± 2 days)		
Safety Assessments											
ECOG Performance Status	X				X				X	X	
PE	X				X				X	X	
Symptom-directed PE		X	X	X		X	X	X			
Weight	X				X				X	X	
Vital Signs ^c	X	X	X	X	X	X	X	X	X	X	
Oxygen Saturation ^c	X				X				X		
ECG ^d	X				X				X	X	

Table 1: On-Treatment Schedule of Activities for BMS-986249 Q8W Dosing Schedule in the Dose Escalation Phase (Part 1) in CA030001

Procedure			cle 1 in length))	Cycle 2 (28 days in length)		Cycles 3 and Beyond (each cycle 28 days in length)	EOT ^{a,b}	Notes		
Trocedure	D1	D8	D15	D22	D1	D8	D15	D22	D1	EOL	Notes
		(± 2 days)	(± 2 days)	(± 2 days)	(± 2 days)	(± 2 days)	(± 2 days)	(± 2 days)	(± 2 days)		
Laboratory Tests	X	X	X	X	X	X	X	X	X	X	There will be a 72-hour window for collection of laboratory tests on D1. If screening laboratory tests are within 72 hours of C1D1, laboratory tests performed at screening can be used for C1D1. Coagulation assessment at screening only. See Section 9.4.4 and Table 9.4.4-1.

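### The two-dose rule for DLT-evaluability cannot be met within the 35-day window by DLT-free Q8W monotherapy participants in Part 1A, and is ambiguous for the Part 1B Q8W combination cohorts

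*Combined protocol and SAP*

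**What the plan says.** Section 7.5.1 gives one DLT period, 5 weeks or 35 days, for monotherapy and combination escalation alike, with no variant for longer dosing intervals. Its evaluability wording uses three different units:

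- Monotherapy (Part 1A): "Participants who have received 2 doses of BMS-986249 and have completed or discontinued due to a DLT in the 5-week DLT period".
- Combination (Part 1B): "Participants receiving either 2 dosing visits of" "BMS-986249 and nivolumab, or participants who discontinued due to a DLT in the 5-week combination treatment DLT period" (one sentence, split by a page break).
- Both parts: participants who "have received less than 2 dosing visits for reasons other than a DLT in both monotherapy and combination therapy" are not evaluable and may be replaced. A further sentence, on delayed dosing, counts two doses of therapy without naming the agent.

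Appendix 12 introduces the Q8W schedule, first used "to evaluate 1600 mg BMS-986249 Q8W monotherapy in Part 1A". Its Table 1 gives BMS-986249 at Cycle 1 and then at every other 28-day cycle from Cycle 3, with nivolumab every cycle in Part 1B. It contains no separate DLT window or evaluability rule. Section 3.2.1.6 lists four Q8W cohorts already dosed: 1,600 mg monotherapy, and 800, 1,200 and 1,600 mg with nivolumab.

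Evaluable counts have work to do. Section 5.1.2.3 triggers the cohort assessment once at least 2 evaluable participants have finished 5 weeks. Section 10.1.1 adds that "At least 6 DLT-evaluable participants will be treated at the BLRM-recommended MTD" and caps each dose level at 12 evaluable participants. Table 10.2-1 defines no DLT-evaluable population, while Table 10.3.2-1 lists the DLT rate by dose level in a section whose analyses all use the treated population.

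**The concern.** The two-dose condition fits Q4W dosing, under which the second dose arrives inside the window. It appears to have been carried over to Q8W unchanged. Applied as written to the Q8W monotherapy cohort, it removes everyone who completed the window without a DLT and leaves at most those who had one. A DLT rate formed on such a set says nothing about the dose.

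Determining the MTD/RP2D is a primary Part 1 objective (Table 4-1), and evaluable counts gate the decisions that lead to it. A reader of the study report needs to know who was in the denominator for each Q8W cohort. The present text gives no usable answer for one cohort and two possible answers for the other three.

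**Working it through.** **Inputs.** DLT window 35 days (Section 7.5.1). Cycle length 28 days; Q8W BMS-986249 at C1D1, C3D1, C5D1; nivolumab at Day 1 of every cycle in Part 1B (Appendix 12, Table 1). Visit window ±2 days except C1D1 (Section 5.1.4). At least 2 evaluable participants for a cohort assessment, with about 3 treated per dose level (Section 5.1.2.3). At least 6 evaluable at the BLRM-MTD and at most 12 per dose level (Section 10.1.1).

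**Step 1: the plan's own rule on Q4W.** 5 × 7 = 35 days. Second dose: 1 + 28 = Day 29, range 27 to 31. This is before Day 35, so two doses fit and the rule works.

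**Step 2: the same rule on Q8W.** Second BMS-986249 dose: 1 + 56 = Day 57. Earliest permitted: 57 − 2 = Day 55, which is 55 − 35 = 20 days after the window closes.

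| Part 1 schedule | BMS-986249 doses by Day 35 | Study-drug dosing visits by Day 35 |
|---|---|---|
| Q4W monotherapy | 2 (Days 1, 29) | 2 |
| Q8W monotherapy | 1 (Day 1) | 1 |
| Q8W BMS-986249 + Q4W nivolumab | 1 (Day 1) | 2 (Day 1 both agents; Day 29 nivolumab only) |

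Q8W monotherapy fails whether doses or dosing visits are counted. Q8W combination passes if any study-drug visit counts, and fails if both agents must be given at each visit.

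**Step 3: consequence for Q8W monotherapy.** Two readings of the monotherapy sentence are possible.

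- If two doses are required even of someone who stops for a DLT, a participant assessed at 5 weeks is never evaluable.
- If a DLT case counts regardless, as the exclusion sentence ("have received less than 2 dosing visits for reasons other than a DLT") implies, only DLT cases are evaluable. With *n* treated and true DLT rate *p*, the evaluable number is then Binomial(*n*, *p*).

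On the second reading with *n* = 3, P(none evaluable) = (1 − p)³ and P(at least 2 evaluable) = 1 − (1 − p)³ − 3p(1 − p)². The plan gives no true DLT rate, so *p* is an assumption, shown over a range:

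| Assumed p | P(none evaluable) | P(at least 2 evaluable) |
|---|---|---|
| 10% | 73% | 3% |
| 16% | 59% | 7% |
| 25% | 42% | 16% |
| 33% | 30% | 26% |

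At 16%: 0.84³ = 0.593; 3 × 0.16 × 0.84² = 0.339; 1 − 0.593 − 0.339 ≈ 0.07. With 12 treated at 16%, the chance of 6 or more evaluable is 0.7%.

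**Step 4: which denominator is affected.** Section 10.1.1 counts its minimum and maximum per dose level in DLT-evaluable participants and says the BLRM uses DLT information from the DLT period only. The evaluable set is therefore taken to be the model's input, although the plan does not say so outright. The DLT rate in Table 10.3.2-1 falls under the treated population and is defined for any Q8W cohort with treated participants.

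**The case against.** **Scope.** A reader might infer that no Q8W participant can be evaluable. The text does not support that. The two-dose condition on BMS-986249 belongs to monotherapy. The combination rule speaks of dosing visits, and the exclusion and delay sentences name no agent, which favours counting the Day 29 nivolumab visit. Three of the four Q8W cohorts are combination cohorts, where the fault is ambiguity. This part of the objection stands.

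**Looser reading.** The monotherapy sentence does not strictly say that both doses must fall inside the window. If a dose on Day 57 counted, DLT-free participants could become evaluable. But evaluability would then be unknown until about 3 weeks after the 5-week assessment in Section 5.1.2.3, and someone who completed the window and stopped before Day 57 would drop out. This reading does not repair the rule.

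**Reported rates and bias.** A reader might infer that the Q8W DLT rates to be reported are undefined or inflated. On the treated denominator in Section 10.3.2 they are neither. For evaluable-based rates, the direction of any distortion depends on which reading was applied, and the documents do not say how Q8W participants were classified. Administrative Letters 03 and 04, which started the Q8W schedules, are not among the documents and may have addressed it.

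**Effect on later dose selection.** A reader might infer that Arm C and Part 2B rest on a faulty Q8W evaluable rate. Sections 5.5.4 and 5.5.6 attribute those choices to overall safety observations, PK, exposure-safety modelling and target-lesion data. The 1,200 mg dose was also given Q4W with nivolumab (Section 3.2.1.6), where the rule works.

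**Safeguards.** Dose decisions also draw on all treated participants and on events after 5 weeks (Sections 5.1.2.3 and 10.1.1). The summary of changes for Amendment 09 records escalation as complete, and Section 3.2.1.6 says no MTD was reached, so the six-participant minimum at the MTD has not come into play. These points limit the consequence but leave the definition wrong for a cohort that was dosed.

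**Conclusion.** The point holds in a limited form. For the Part 1A 1,600 mg Q8W cohort the evaluability rule cannot be met by a DLT-free participant at the 5-week assessment: one BMS-986249 dose falls in the window and the second comes at least 20 days after it closes. For the three Part 1B Q8W cohorts the rule can be read as met or not met, depending on whether a nivolumab-only visit counts.

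What is affected is the evaluable count behind cohort decisions and, by implication, the BLRM input. The probabilities above rest on assumed DLT rates of 10% to 33%, about 3 treated participants, and the reading under which DLT cases always count. They describe the rule as written, not what happened in the trial. Neither actual bias nor an effect on the regimens taken into Part 2 is shown.

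**What to change.** In Section 7.5.1 and in the SAP, define a DLT-evaluable participant as one who received all study-drug doses scheduled within the 35-day window for the assigned schedule and completed the window, or who had a DLT within it. Add this population to Table 10.2-1. Reconcile the dose, dosing-visit and delayed-dose wording in Section 7.5.1 with the Q8W schedule in Appendix 12 and with the treated-population denominator in Section 10.3.2.

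In the study report, state how Q8W participants were classified when cohort decisions were made, give Q8W DLT counts over both treated and evaluable denominators, and present the BLRM summary on the stated definition.

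The cost is small: one definition, one table row, and a re-run of the Part 1 DLT table and BLRM summary. No new data are needed, and Section 10.3 has the SAP finalised before database lock.
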